10.3.4.4. Gastrointestinal Safety

Because GI AEs, including nausea, vomiting, and diarrhea, are among the most common events reported in patients treated with dulaglutide, summaries and analyses for incidence, time to onset, duration, and severity of nausea and vomiting may be provided for each treatment during the weeks of dose escalation, during the period on the final assigned dose, and overall, to compare the effects of the 3 different doses on GI tolerability, as well as the overall effects of randomized therapies.

10.3.4.5. Laboratory Analyses

Laboratory safety measurements will be summarized. For continuous (numeric) laboratory analytes, the change from baseline by visit will be summarized as detailed in Section 10.3.1. Change from baseline to endpoint (LOCF) will be analyzed using an ANOVA on the ranks with treatment as a fixed effect unless otherwise specified. For subjective (qualitative) laboratory analytes, counts and percentages of patients with normal and abnormal values will be analyzed using Fisher's exact test.

Shift tables of the change from baseline value to the most extreme postbaseline value and from baseline to Week 52 for selected analytes using clinically meaningful thresholds will be summarized.

10.3.4.6. Vital Signs

Descriptive statistics for the actual measurements and changes from baseline for SBP and DBP, PR, and rate-pressure product (RPP; $SBP \times PR / 1000$) will be presented by treatment and visit.

Vital signs will be analyzed using a similar MMRM-based model as that described in Section 10.3.1 for continuous variable analyses.

10.3.4.7. Electrocardiograms

Descriptive statistics for the absolute measurements, changes from baseline, and clinically relevant changes for selected ECG parameters defined in the SAP, including QT corrected for heart rate (HR) using Fridericia's formula (QTcF), will be presented by treatment and visit. These parameters will be analyzed using a similar MMRM as that described in Section 10.3.1 for continuous variable analyses.

10.3.5. Pharmacokinetic/Pharmacodynamic Analyses

Population PK analyses will be conducted using dosing data and dulaglutide concentrations obtained from all patients via commonly accepted pharmacostatistical methods (for example, nonlinear mixed-effects modeling), and covariate screening. If necessary, data from this study may be combined with data from previous study/studies for analysis, or prior population PK or PK/PD model information from previous studies may be utilized to initiate analysis.

The relationships between dulaglutide doses and/or concentrations and key safety measures (such as QT interval, PR interval, and HR), tolerability measure (such as nausea and vomiting), and efficacy measures (such as fasting glucose, HbA1c, and weight) will be assessed either graphically or through modeling. Endpoints may include but are not necessarily limited to those listed above.

In addition, if positive antibody titers to dulaglutide are observed, the impact of antibody formation on PK exposures, dulaglutide clearance, and if applicable, drug effect(s) will be evaluated.

10.3.6. Other Analyses

10.3.6.1. Health Economics

Continuous measures from the patient reported outcomes (PRO) instruments will be analyzed using the MMRM model specified in Section 10.3.1, using on-treatment without rescue data.

Categorical measures from the PRO instruments will be summarized for each treatment.

10.3.6.2. Subgroup Analyses

Subgroup analyses of treatment interaction with important factors, including age (<65 years, ≥65), race, gender, country, duration of diabetes, baseline HbA1c (<8.5% [69 mmol/mol], ≥8.5% [69 mmol/mol]), body weight, and BMI may be conducted for the primary endpoint of HbA1c.

These will be conducted using the MMRM with treatment, visit, subgroup, treatment-by-visit, treatment-by-subgroup, visit-by-subgroup, and treatment-by-visit-by-subgroup as fixed effects, and baseline as covariate. If the MMRM fails to converge, the corresponding ANCOVA or ANOVA model (LOCF) will be used.

When analyzing baseline HbA1c as a subgroup, the baseline HbA1c will not be included as a covariate to avoid collinearity.

Other exploratory subgroup analyses may be performed as deemed appropriate.

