3.2. Background

Pharmacokinetic (PK)/pharmacodynamics (PD) modeling from original Phase 1-2 dulaglutide studies suggested a dose-dependent incremental benefit with dulaglutide versus currently approved doses on HbA1c and body weight reduction. Phase 2 Study H9X-MC-GBGJ (GBGJ) was recently conducted to assess the safety and efficacy of once weekly dulaglutide 3.0 mg and 4.5 mg in comparison to placebo in 317 patients with T2D treated with metformin monotherapy, with exploratory comparisons to dulaglutide 1.5 mg (the highest dose approved by regulatory agencies). Data from Study GBGJ provided evidence for incremental efficacy of these higher doses of dulaglutide versus 1.5 mg once weekly on glycemic control and body weight reduction, particularly at higher baseline HbA1c levels, with an acceptable tolerability and safety profile at both higher doses. The trial results also suggested stepwise titration of dulaglutide dose was associated with acceptable tolerability of the 2 higher doses.

Further study of higher doses of dulaglutide also was assessed in context with prior dose-finding studies. The currently approved dulaglutide doses (0.75 mg and 1.5 mg once weekly) were selected in the Phase 2/3 Study H9X-MC-GBCF (GBCF), which initially included doses up to 3.0 mg once weekly (Skrivanek et al. 2014). The purpose of the first stage of Study GBCF was to identify an optimal dose using prespecified measures of efficacy (HbA1c and weight) and safety (diastolic blood pressure [DBP] and heart rate [HR]). Following a number of interim data reviews, the Data Monitoring Committee (DMC) recommended discontinuing the dulaglutide 3.0 mg dose because of higher incidence in pancreatic enzyme values above upper limit of normal (ULN) (with or without abdominal pain or suspected pancreatitis), increases in HR, and higher incidence of gastrointestinal (GI) adverse events (AEs) (Skrivanek et al. 2014).

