5.5. Justification for Dose and Dose Escalation Regimen

The investigational dulaglutide doses (3.0 mg and 4.5 mg) were selected considering adequate separation in PK exposure range between the doses and 1.5 mg to enable evaluation of their efficacy and adverse effect profiles. Ratios of mean area under concentration-time curve (AUC) for 3.0 mg/4.5 mg doses to 1.5 mg dose are 2.26 and 3.10, respectively. The steady-state mean AUC and 90% confidence intervals (CIs) for the 1.5 mg, 3.0 mg, and 4.5 mg doses are 11,800 (5300, 21,300), 26,700 (15,300, 41,400), and 36,600 (21,100, 56,500) ng.h/mL, respectively. Therefore, the ratio of mean AUC for 4.5 mg to 3.0 mg is anticipated to be 1.37. Based on predicted plasma exposures in patients with T2D receiving the highest investigational dulaglutide dose of 4.5 mg, the margins of safety (ie, plasma exposure multiples at the no-observed-adverse-effect level [NOAEL]) in chronic toxicology studies in monkeys and rats were 162-fold and 55-fold, respectively.

Data from Phase 2 Study GBGJ provided evidence for incremental efficacy of dulaglutide 3.0 mg and 4.5 mg once weekly versus 1.5 mg once weekly on glycemic control and body weight reduction. After 18 weeks of treatment (analysis of on-treatment data without rescue), the estimated treatment differences in HbA1c reduction with 3.0 mg and 4.5 mg once weekly relative to 1.5 mg once weekly were -0.22% and -0.26%, respectively. Larger differences were observed in subgroups of patients with higher baseline HbA1c (ie, $\geq 8.5\%$ [69 mmol/mol] vs. $< 8.5\%$ [69 mmol/mol]). Dulaglutide 3.0 mg and 4.5 mg once weekly also provided for additional body weight reduction over the 1.5 mg dose that exceeded 1 kg at Week 18, with further weight reduction expected with longer durations of treatment. Although the effects of dulaglutide 4.5 mg were generally greater than the effects of the 3.0 mg dose on measures of glycemic control and body weight, a larger study is required to fully characterize the benefit/risk profile of each higher dulaglutide dose compared with the 1.5 mg dose over a longer duration of treatment.

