10.3. Statistical Analyses

10.3.1. General Statistical Considerations

Statistical analysis of this study will be the responsibility of Eli Lilly and Company or its designee. Any change to the data analysis methods described in the protocol will require an amendment ONLY if it changes a principal feature of the protocol. Any other change to the data analysis methods described in the protocol, and the justification for making the change, will be described in the statistical analysis plan (SAP) or the clinical study report (CSR). Additional exploratory analyses of the data may be conducted as deemed appropriate.

Table GBGL.4 defines the populations to be used for analyses.

Efficacy and safety analyses will be conducted in the Intent to Treat (ITT) Population. There will be 2 primary estimands to compare treatment groups in terms of the primary measure of HbA1c change from baseline to Week 36.

One primary estimand will be an efficacy estimand (*de jure* effect) which will use the data collected before initiation of any rescue medication or premature treatment discontinuation to demonstrate the effect of treatment and avoid confounding effects of other antihyperglycemic agents (Little and Kang, 2014). The other primary estimand will be a treatment-regimen estimand (*de facto* effect) which will include data collected after initiation of other antihyperglycemic therapy and/or after premature treatment discontinuation.

The treatment-regimen (*de facto*) estimand is included as primary at the request of the US Food and Drug Administration (FDA). The efficacy (*de jure*) estimand will be considered primary for all other purposes, and will be applied to all efficacy outcomes unless otherwise specified to demonstrate effect of treatment and avoid confounding effects with other antihyperglycemic agents.

Both estimands will be tested at the full significance level of 0.05.

Analyses of safety parameters, except for hypoglycemia events, will be conducted in the ITT Population unless otherwise specified.

Unless otherwise noted, all tests of treatment effects will be conducted at a 2-sided alpha level of 0.05, and CIs will be calculated at 95%, 2-sided. All tests of interactions between treatment groups and other factors will be conducted at a 2-sided alpha level of 0.10.

The baseline will be at the randomization visit (Visit 3). If baseline data are missing, the last nonmissing measurement taken prior to Visit 3 will be used.

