6.12. Subgroup Analyses

Subgroup analyses of the treatment interaction for important factors, including age group (<65 years, ≥65), race, gender, country, duration of diabetes (<median, ≥median), baseline HbA1c (<8.5%, ≥8.5%), body weight (<median, ≥median), and body mass index (<median, ≥median), may be conducted for the primary endpoint of HbA1c. Country will use the pooled country.

These analyses will be conducted using the MMRM with treatment, visit, subgroup, treatment-by-visit, treatment-by-subgroup, visit-by-subgroup, and treatment-by-visit-by-subgroup as fixed effects, and baseline as a covariate. If the MMRM fails to converge, the corresponding ANCOVA or ANOVA model (LOCF) will be used.

When analyzing baseline HbA1c as a subgroup, the baseline HbA1c will not be included as a covariate to avoid colinearity.

Treatment-emergent AEs occurring in >5% of patients will be summarized descriptively for the patients with the top quartile of body weight reduction from baseline by treatment group.

Other exploratory subgroup analyses may be performed as deemed appropriate.

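### The exploratory treatment-by-baseline-HbA1c interaction is prespecified only as a split at 8.5%; if effect modification is roughly linear, a continuous interaction would have clearly more power

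*Protocol*

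**What the plan says.** Protocol 10.3.6.2 (Subgroup Analyses) allows treatment-interaction analyses of the primary endpoint for a list of factors, "including age (<65 years, ≥65), race, gender, country, duration of diabetes" among them, and continues with "baseline HbA1c (<8.5% [69 mmol/mol], ≥8.5% [69 mmol/mol]), body weight, and BMI may be conducted for the primary endpoint of HbA1c". In the protocol only age and baseline HbA1c have cut points. SAP 6.12 supplies the rest: "duration of diabetes (<median, ≥median), baseline HbA1c (<8.5%, ≥8.5%), body weight (<median, ≥median), and body mass index (<median, ≥median".

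Both sections use an MMRM with treatment, visit, subgroup and all their interactions. Protocol 10.3.1 sets the test level: "All tests of interactions between treatment groups and other factors will be conducted at a 2-sided alpha level of 0.10". For HbA1c itself both sections add a restriction, in the protocol's words: "When analyzing baseline HbA1c as a subgroup, the baseline HbA1c will not be included as a covariate to avoid collinearity".

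The sponsor gives a reason to look at baseline HbA1c. Protocol 3.2 describes the Phase 2 incremental efficacy as present "particularly at higher baseline HbA1c levels". Protocol 5.5 says "Larger differences were observed in subgroups of patients with higher baseline HbA1c" and defines higher as 8.5% or above. Randomization is stratified at the same value (Protocol 7.2, SAP 5.3).

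**The concern.** Entry HbA1c runs from 7.5% to 11.0%. A split at 8.5% treats 8.4% and 8.6% as different, and 8.6% and 10.9% as the same. If the added benefit of 3.0 mg and 4.5 mg rises gradually with starting HbA1c, this is an inefficient test of it. The planned HbA1c model also leaves variation in baseline HbA1c within each stratum in the residual, because the continuous covariate is removed.

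At stake is how well the trial can follow up the one effect-modification signal that the documents report. A real gradient is more likely to be missed with the planned model than with one that is equally easy to fit.

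**Working it through.** **The plan's own figure.** The documents give no power for interaction tests. Their primary power (difference 0.22, SD 1.1, 510 completers per arm from 600 × 0.85) reproduces: 0.22 / (1.1 × √(2/510)) = 3.19. This gives 89.1% per dose at 0.05, 83.0% at 0.025, and 93.1% for at least one dose (correlation 0.5), in line with the stated 80% or more.

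**Information kept by a split.** For a linear modifier, this is the squared correlation between the two-group indicator and the continuous covariate. For a normal covariate with a share p on one side of the cut it equals φ(z_p)² / [p(1−p)]:

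- p = 0.5: 0.3989² / 0.25 = 0.637
- p = 0.4: 0.622
- p = 0.2: 0.490

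The documents give no covariate distributions, so the following rest on assumed shapes:

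- HbA1c cut at 8.5%, several shapes bounded to 7.5-11.0%: 57-68% kept, equivalent to about 581-694 of the 1020 completers in one dose comparison (1020 × 0.57 and × 0.68)
- Age cut at 65, with 16-31% of patients above: 44-58%
- BMI at the median, truncated near 25: 65-66%
- Right-skewed duration at the median: about 37-55%
- A uniform covariate at its median: 75%
- A true step at the cut: no loss

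**Power for HbA1c.** The comparison is one dose against 1.5 mg at Week 36, 510 per arm, 2-sided 0.10 (critical value 1.645). Assumptions: baseline SD 0.82, residual SD 1.0 to 1.1 given baseline (the documents' 1.1 is the SD of the change), prognostic slope −0.6, information kept 0.62, and slope difference s per 1% HbA1c.

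- Continuous model: signal-to-error ratio = s × 0.82 / (σ√(2/510)).
- Planned split model, covariate dropped: residual SD becomes σ′ = √(σ² + 0.6² × (1 − 0.62) × 0.82²) = √(σ² + 0.092), that is 1.045 for σ = 1.0 and 1.141 for σ = 1.1. The ratio = s × 0.82 × √0.62 / (σ′√(2/510)).

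Example with s = 0.20 and σ = 1.0. Continuous: 0.164 / 0.0626 = 2.62, power 84%. Split: 0.1291 / 0.0654 = 1.97, power 63%.

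| Slope s | Continuous, formula (σ 1.1 to 1.0) | Continuous, simulated | Planned split, formula | Planned split, simulated |
|---|---|---|---|---|
| 0.10 | 33-37% | 34-38% | 24-26% | 23-26% |
| 0.15 | 56-63% | 57-63% | 39-44% | 38-42% |
| 0.20 | 77-84% | 77-84% | 57-63% | 57-63% |

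With no interaction, the tests reject in about 10% of simulated trials, as they should. Most of the loss comes from the split. At residual SD 1.0, keeping continuous HbA1c as a covariate beside the split gives about 29%, 45% and 67%, only 3 to 4 points above the planned model.

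**The case against.** The strongest reply is that the split matches the evidence. The Phase 2 signal was itself a two-group comparison at 8.5%, and 8.5% is the randomization stratum, so the planned analysis directly replicates that signal. This stands, and it is why the split should stay. A reader might infer from Protocol 3.2 and 5.5 that Phase 2 showed a gradient. The documents do not say so; linearity is an assumption here.

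The slopes also have no source in the documents, and the largest is strong. With a mean difference of 0.22 and a slope of 0.20, the added benefit vanishes 1.1 points below the mean baseline (0.22 / 0.20), at about 7.8% if that mean is 8.9% (assumed). At the two smaller slopes the continuous test also stays below 80%, so a non-significant result would remain inconclusive either way.

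Effect modification is not a listed objective, the analyses are optional, and no claim depends on them. Both subgroup sections permit further exploratory subgroup analyses, and SAP 6.1 permits additional analyses without revision. Protocol 10.3.5 plans exposure-response modeling with covariate screening. These leave room for a continuous analysis but do not prespecify a test of randomized treatment by continuous baseline value.

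Finally, the Phase 2 rationale covers HbA1c only. Nothing in the documents singles out age, duration, weight or BMI as modifiers.

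**Conclusion.** The point holds as a modest efficiency improvement to an exploratory analysis. Under a roughly linear gradient, the 8.5% split keeps about 57-68% of the information. The planned model then has about 11-12, 19-21 and 20-21 percentage points less power than a continuous interaction at slopes of 0.10, 0.15 and 0.20. These figures rest on the assumed slopes, baseline SD, residual SD and prognostic slope, and on a single-time-point comparison of one dose with 1.5 mg.

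Three stronger readings are not supported. A reader might infer that splitting always discards a third or more of the information; the loss is 25% for a uniform covariate cut at its median, and zero for a step at the cut. A reader might infer that a non-significant test will be reported as absence of interaction; neither document says that. A reader might infer that the trial's main results are weakened; the primary and key secondary analyses and their power are unaffected.

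**What to change.** In SAP 6.12 and Protocol 10.3.6.2:

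1. Keep the estimates and confidence intervals for the two HbA1c groups at 8.5%.
2. Name as the interaction test the Week 36 contrast of treatment by continuous baseline HbA1c, from the MMRM with treatment-by-visit-by-covariate terms, at the 0.10 level already stated.
3. Add a quadratic term as a check of linearity.
4. State that the sentence dropping baseline HbA1c as a covariate applies to the split model only. Otherwise the section would contradict the continuous model.
5. Optionally, add the same continuous test for age, duration, weight and BMI. The case is weaker there, since no Phase 2 signal is reported for them.

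The cost is a text edit and a few extra model runs, with no new data and no change to alpha. The downside is reliance on a roughly linear gradient. A true step at 8.5% would show better in the split, which is retained.

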10.3.7. Evaluation of Immunogenicity

The frequency and percentages of patients with preexisting (baseline) ADA and with TE ADA to dulaglutide will be tabulated. For patients with ADA detected at baseline, TE ADA are defined as those with a 4-fold (2 dilutions) increase in titer compared to baseline. The frequency of neutralizing antibodies with specificity for dulaglutide and with specificity for native-sequence GLP-1 will also be tabulated in patients with TE ADA detected.

The relationship between the presence of antibodies and the PK parameters and PD response including safety and efficacy to dulaglutide may be assessed.

10.3.8. Interim Analyses

No interim analyses of efficacy are planned for this study. If an unplanned interim analysis is deemed necessary, the appropriate Lilly medical director, or designee, will be consulted to determine whether it is necessary to amend the protocol.

An independent DMC will have the responsibility to review unblinded interim analysis results in order to monitor the safety of the patients in the study up until the last patient completes the Week 36 visit (Visit 9). The detailed analysis and communication plan for the interim analyses will be defined in a separate DMC charter. An internal Statistical Analysis Center (SAC) external to the study team will perform the data analysis for the DMC. As no efficacy analyses are planned by the DMC, the Family-Wise Error Rate will not be affected by any of these interim analyses; hence, no alpha spending is necessary.

Only the DMC will be authorized to evaluate unblinded interim safety analyses. Study sites will receive information about interim results ONLY if deemed necessary for the safety of their patients.

The DMC will perform the first safety analysis after approximately 900 patients (50% of the planned sample size) have the opportunity to complete Visit 7 (Week 18) or approximately 7 months after the first patient is randomized (whichever comes first). A second safety review will be planned after approximately 900 patients have the opportunity to complete Visit 9 (Week 36), or approximately 12 months after the first patient is randomized (whichever comes first). The number and timing of the DMC interim analyses may be adjusted by the actual enrollment rate. This adjustment will not require a protocol amendment.

There may be 2 database locks for this study. A primary database lock may be conducted for all data accumulated through the time when all randomized patients have completed 36 weeks of treatment (Visit 9, primary objective endpoint). The final database lock will be conducted for all data accumulated through the time when all patients have completed the 4-week Safety Follow-Up Period (through Visit 801). For the primary database lock, all efficacy analyses will be conducted based on Week 36 (Visit 9). If a decision is made to only conduct the final database lock and not the primary lock, it will be documented without an amendment to the protocol.

Appendix 1. Abbreviations and Definitions

Term	Definition
ADA	anti-drug antibodies
AE	adverse event: Any untoward medical occurrence in a patient or clinical investigation subject administered a pharmaceutical product that does not necessarily have a causal relationship with this treatment. An adverse event can therefore be any unfavorable and unintended sign (including an abnormal laboratory finding), symptom, or disease temporally associated with the use of a medicinal (investigational) product, whether or not related to the medicinal (investigational) product.
AESI	adverse event of special interest
ALT	alanine aminotransferase
ANCOVA	analysis of covariance
ANOVA	analysis of variance
APPADL	Ability to Perform Physical Activities of Daily Living
AST	aspartate aminotransferase
AUC	area under concentration-time curve
blinding/masking	
A single-blind study is one in which the investigator and/or his staff are aware of the treatment but the patient is not, or vice versa, or when the sponsor is aware of the treatment but the investigator and/his staff and the patient are not.
 
A double-blind study is one in which neither the patient nor any of the investigator or sponsor staff who are involved in the treatment or clinical evaluation of the patients are aware of the treatment received.

BMI	body mass index
BP	blood pressure
CEC	Clinical Endpoint Committee
CI	confidence interval
CKD-EPI	Chronic Kidney Disease-Epidemiology
complaint	A complaint is any written, electronic, or oral communication that alleges deficiencies related to the identity, quality, purity, durability, reliability, safety or effectiveness, or performance of a drug or drug delivery system.
CRP	clinical research physician: Individual responsible for the medical conduct of the study. Responsibilities of the CRP may be performed by a physician, clinical research scientist, global safety physician, or other medical officer.

CSR	clinical study report
CT	computed tomography
CV	cardiovascular
DBP	diastolic blood pressure
DID-EQ	Diabetes Injection Device Experience Questionnaire
DMC	Data Monitoring Committee
DPP-4	dipeptidyl peptidase-4
ECG	electrocardiogram
eCRF	electronic case report form
eGFR	estimated glomerular filtration rate
enroll	The act of assigning a patient to a treatment. Patients who are enrolled in the trial are those who have been assigned to a treatment.
enter	Patients entered into a trial are those who sign the informed consent form directly or through their legally acceptable representatives.
ERB	Ethics Review Board
ESRD	end-stage renal disease
ET	early termination
FDA	Food and Drug Administration
FPG	fasting plasma glucose
FSG	fasting serum glucose
GCP	good clinical practice
GGT	gamma glutamyl-transferase
GI	gastrointestinal
GLP-1	glucagon-like peptide-1
GLP-1 RA	glucagon-like peptide-1 receptor agonist
HbA1c	hemoglobin A1c
HOMA2	Homeostasis Model Assessment-2
HOMA2-%B	β -cell function as measured by the HOMA2 method

HOMA2-IR	insulin resistance as measured by the HOMA2 method
HR	heart rate
IB	Investigator's Brochure
ICF	informed consent form
ICH	International Conference on Harmonisation
interim analysis	An interim analysis is an analysis of clinical study data, separated into treatment groups, that is conducted before the complete reporting database is created/locked for the primary endpoint.
investigational product	A pharmaceutical form of an active ingredient or placebo being tested or used as a reference in a clinical trial, including products already on the market when used or assembled (formulated or packaged) in a way different from the authorized form, or marketed products used for an unauthorized indication, or marketed products used to gain further information about the authorized form.
ITT	intent to treat: The principle that asserts that the effect of a treatment policy can be best assessed by evaluating on the basis of the intention to treat a patient (that is, the planned treatment regimen) rather than the actual treatment given. It has the consequence that patients allocated to a treatment group should be followed up, assessed, and analyzed as members of that group irrespective of their compliance to the planned course of treatment.
IW-SP	Impact of Weight on Self-Perceptions Questionnaire
IWRS	interactive web-response system
LOCF	last observation carried forward
LS mean	least-squares mean
MAR	missing at random
MedDRA	Medical Dictionary for Regulatory Activities
MI	myocardial infarction
MMRM	mixed-model repeated measures
MRI	magnetic resonance imaging
MTC	medullary thyroid carcinoma
NAFLD	nonalcoholic fatty liver disease
NOAEL	no adverse effect level
NRC	National Research Council
OAM	oral antihyperglycemic medication

OTC	over-the-counter
PD	pharmacodynamic
PG	plasma glucose
PK	pharmacokinetics
PMM	pattern-mixture model
PP	per-protocol set: The set of data generated by the subset of patients who sufficiently complied with the protocol to ensure that these data would be likely to exhibit the effects of treatment, according to the underlying scientific model.
PR	pulse rate
PRO	patient reported outcome
QTcF	QT corrected for heart rate using Fridericia's formula
REML	restricted maximum likelihood
RPP	rate-pressure product
SAC	Statistical Analysis Center
SAE	serious adverse event
SAP	statistical analysis plan
SBP	systolic blood pressure
screen	The act of determining if an individual meets minimum requirements to become part of a pool of potential candidates for participation in a clinical study.
SD	standard deviation
SDP	single-dose pen
SGLT2	sodium-glucose co-transporter 2
SmPC	Summary of Product Characteristics
SMPG	self-monitored plasma glucose
SOC	system organ class
SUSARs	suspected unexpected serious adverse reactions
T1D	type 1 diabetes
T2D	type 2 diabetes mellitus
TE	treatment-emergent

TEAE	treatment-emergent adverse event: An untoward medical occurrence that emerges during a defined treatment period, having been absent pretreatment, or worsens relative to the pretreatment state, and does not necessarily have to have a causal relationship with this treatment.
ULN	upper limit of normal
US	United States
USPI	United States Package Insert
VAS	Visual Analog Scale
WHO	World Health Organization

